14.6 Safety Reporting

The Sponsor is responsible for performing ongoing safety evaluation in this study protocol. Sponsor activities regarding safety include:

- classification of all AEs,
- review of all AEs reported in the study,

- confirm site's classification of AEs in terms of severity and relatedness to the study device and/or study procedure,
- review of severity and relatedness with the study Investigator, especially when there is disagreement between the Investigator and the Sponsor,
- review of device deficiencies and malfunctions, including determination and documentation of whether deficiencies/malfunctions could have led to an AE or SAE,
- ensuring the reporting of all SAEs and device deficiencies/malfunctions that could have led to an AE or SAE to the IRB and, if required, regulatory authorities in a timely fashion,
- informing all site Investigators in writing of all SAEs at all sites in a timely fashion and
- updating the risk analysis and assessment of corrective or preventive actions potentially required as a result of new information obtained in the investigation

The Sponsor will evaluate all serious adverse events against US reporting requirements (Medical Device Reporting, 21 CFR 812) and Medical Device Directive (vigilance incident reporting) as per its standard operating procedures. The Sponsor will investigate each SAE to determine whether the event represents an unanticipated serious adverse device effect (USADE, see Section 12.1.2). The Sponsor will report any event to regulatory authorities, Investigators and reviewing IRBs/ECs as necessary. If an investigation shows that a USADE presents an unreasonable risk to subjects, the Sponsor will terminate all investigations or parts of investigations presenting that risk as soon as possible. The Sponsor will only resume a terminated investigation after corrective actions have taken place, site Investigators are informed and IRBs/ECs have been notified and given approval to resume the study.

14.7 Case Report Forms

Case Report Forms (CRFs) will be provided in order to collect required data points. Data will be routinely monitored and collected by the sponsor, or designee, to identify inconsistent or missing data and to ensure compliance with the study protocol.

An CRF is required and should be completed for each randomized Subject. The Investigator has ultimate responsibility for the collection and reporting of all data entered on the CRFs and any other data collection forms (source documents) and ensuring that they are accurate, authentic/original, attributable, complete, consistent, legible, timely (contemporaneous), enduring and available when required. The CRFs must be signed by the Investigator to attest that the data contained therein are true. Investigators will be responsible for the accurate and timely completion of CRFs during the trial.

14.8 Quality Assurance Audits

Sponsor representatives or designees may conduct site quality assurance (QA) audits during the study. The Investigator must agree to provide the auditor with direct access to all relevant documents and discuss any findings with the auditor.

In the event of an inspection by the FDA or other regulatory authorities, the Investigator must give the inspector direct access to relevant documents and to discuss any findings with the inspector. The Investigator must notify Myoscience, Inc. in the event of a FDA site audit.

14.9 Confidentiality

The Investigator is responsible for ensuring the confidentiality of subjects throughout the trial. A unique identification code will be assigned to each Subject participating in this trial. Any data that may be published in abstracts, scientific journals, or presented at medical meetings will reference a unique subject code and will not reveal the subject's identity.

14.10 Records Retention

The Investigator must maintain all study records (including device disposition, informed consents, source documents, correspondence, regulatory documents, contracts etc.) for at least 2 years after study completion. At the Investigator's discretion, all records may be sent to the Sponsor for permanent storage.

The Investigator must contact the Sponsor or designee prior to destroying any records associated with this study. If the Investigator withdraws from the study, all study-associated records must be transferred to a mutually agreed upon designee. Written notification of such a transfer must be given to the Sponsor or designee.

14.11 Publication and Reporting of Study Results

The study will be registered with clinicaltrials.gov before the first patient is treated. Study results will be documented in a study report that will be signed by Myoscience representatives and by the Principal Investigator of the entire Study. Individual site Principal Investigators will not be required to sign this report.

The results of this Myoscience sponsored study will be published in accordance with standard editorial and ethical practices. Results from multi-center studies must be published or presented at congresses only in their entirety with data pooled from all centers. Individual Investigators may not publish data from individual centers, unless granted specific written permission by Myoscience to do so.

The list of authors of any formal publication or presentation of study results may include, as appropriate, representatives of Myoscience.

## List of Abbreviations

AE	Adverse Event
AFCN	Anterior Femoral Cutaneous Nerve
AUC	Area Under the Curve
ISN	Infrapatellar branch of the Saphenous nerve
ITT	Intent-to-Treat
IV	Intravenous
KOOS JR.	Knee Injury and Osteoarthritis Outcomes Score
MedDRA	Medical Dictionary for Regulatory Activities
NRS	Numeric Rating Scale
NSAID	Non-Steroidal Anti-Inflammatory Drug
PCA	Patient-Controlled Analgesia
[REDACTED]	[REDACTED]
SAE	Serious Adverse Event
SAS	Statistical Analysis System
SOC	System Organ Class
TEAE	Treatment Emergent Adverse Event
TKA	Total Knee Arthroplasty
TME	Total daily Morphine Equivalent
TUG	Timed Get Up and Go

## 1.0 INTRODUCTION

This document details the analysis plan for the study entitled “A Post-Market, Prospective, Randomized, Controlled Study to Evaluate the iovera° Device in Treating Pain Associated with Total Knee Arthroplasty”. It describes the proposed efficacy and safety analyses, including planned summary tables and by-subject data listings.

Total Knee Arthroplasty (TKA) is a highly effective procedure to relieve symptoms in patients with severe arthritis. Improvements in pain, physical function, and enhanced quality of life in patients who have undergone TKA are well established in the literature. However, post-operative pain associated with TKA is severe. Effective pain control following TKA allows for earlier ambulation and initiation of physical therapy, which speeds recovery, reduces hospital length of stay, and decreases the risk of postoperative complications. The Veterans Health Administration/Department of Defense and the American Society of Anesthesiologists have both issued guidelines suggesting that wherever possible, practitioners should use multimodal pain management. Clinical management of post-op TKA pain should include both pharmacologic and non-pharmacologic modalities and minimize preventable postoperative complications. As demand for primary TKAs is projected to grow to 3.48 million procedures per year by 2030 in the United States alone, the need for effective and economic multi-modal pain management has never been greater.

Managing pain via multi-modal strategies, including peripheral nerve blocks, in the inpatient postoperative phase has been shown to decrease opioid consumption, decrease opioid related side effects, decrease hospital stay, and increase time to ambulation. Nursing, hospital, and pharmacy utilization in managing PCA, continuous regional nerve blocks, and administration of oral opioid dosing are associated with higher costs of care and introduce sources for staff error. Furthermore, the idea of multi-modal pain management extends beyond the in-patient phase of treatment. Decreasing prescription opioid use during outpatient rehabilitation decreases NSAID and opioid related side effects, especially important among the aging population.

The iovera° device introduces a new mode of pain management delivery in TKA. The iovera° system uses liquid nitrous oxide contained within the device and closed-end needles to create a precise zone of cold at the target nerve sites. This Focused Cold TherapyTM delivery platform causes a temporary peripheral nerve block based on a process called Wallerian degeneration (2nd degree axonotmesis) without disrupting connective nerve tissue. With nerve conduction blocked, pain is relieved in sensory nerves (nerves that pass impulses from receptors toward or to the central nervous system). Degeneration of the nerve axons is followed by a predictable restoration of nerve function involving axon regeneration from the point of treatment to the distal end of the nerve at a rate of 1.0–1.5 mm a day. Early clinical study results have demonstrated that the duration of effect of iovera°, when applied to the infrapatellar branch of the saphenous nerve for knee pain, is two to three months; longer than that of other clinically adopted modalities (PCA opioids, single shot regional nerve blocks, continuous regional nerve blocks, extended-release peri-operative local opioids, oral and IV NSAIDs, acetaminophen, and oral opioids). Early clinical data further suggests that iovera°, when applied to the infrapatellar branch of the saphenous nerve (ISN) and anterior femoral cutaneous nerve (AFCN) prior to TKA, reduces the amount of opioids requested by subjects to maintain similar levels of pain relief.

This study is designed to investigate whether iovera° treatment prior to TKA decreases cumulative patient opioid use over the course of 6 weeks following TKA while maintaining similar levels of pain relief. The study will also investigate whether there is a relationship between patients treated with iovera° and patient reported pain and function as measured by KOOS JR., Numeric Rating Scale (NRS) for Pain [REDACTED]  
[REDACTED]

## **2.0 STUDY OBJECTIVE**

The objective of the study is to evaluate the outcomes of patients undergoing iovera® treatment of the ISN and AFCN prior to total knee arthroplasty to provide temporary postoperative pain relief.

## 3.0 STUDY DESIGN

### 3.1 Overview

This is a single-site, prospective, randomized trial. The study's schedule of assessments is shown in Table 1.

**Table 1. Schedule of Assessments**

Assessment	Visit 1 / Screening	Visit 2 / iovera ° Treatment	Visit 3 / DAY OF TKA (Day 0)	Visit 4 / 72 Hours Post-op	Visit 5 / 2 Weeks Post-op	Visit 6 / 6 Weeks Post-op	Visit 7 / 12 Weeks Post-op
Informed Consent	X						
Eligibility	X	X					
Medical history	X	X					
Concomitant Medication Assessment	X	X	X	X	X	X	X
Prior/Concurrent Therapy	X	X		X	X	X	X
Randomization*	X						
Study Treatment		X					
Physical Exam	X						
Vital Signs	X	X					
Knee Circumference	X						
KOOS JR. Questionnaire	X			X	X	X	X
NRS for Pain	X			X	X	X	X
Subject Satisfaction Questions						X	X
Physical Performance Measures	X				X	X	X
Pain Medication Accountability				X	X	X	X
AE/SAE Assessment		X	X	X	X	X	X

\* Randomization occurs after the subject has met eligibility criteria

### 3.2 Method of Assigning Subjects to Treatment

After meeting all of the inclusion and none of the exclusion criteria and prior to study treatment, subjects will be randomized in a 1:1 manner to either:

- **iovera° Treatment:** Subject undergoes treatment with the study device using study supplied Smart Tip.
- **Standard of Care Treatment:** Subject does not undergo iovera° Treatment

The Investigator or designee will record the randomization assignment in the source documentation and CRF.

### **3.3 Blinding**

This is an unblinded study.

### **3.4 Determination of Sample Size**

The sample size was determined based on the primary effectiveness endpoint, the cumulative consumption of opioids from the time of hospital discharge to 6 weeks post-TKA Surgery. Opioid consumption will be converted to morphine equivalents, and subject consumption will be verified by pill count at follow-up visits. The cumulative morphine equivalent will be divided by the number of days to provide the Total Daily Morphine Equivalent (TME) for the subject. Let  $\mu_{1,Active}$  and  $\mu_{1,SOC}$  denote the true mean TMEs for the active and standard of care treatments, respectively. The required sample size was determined based on providing at least 80% power for the primary effectiveness endpoint using a one-sided, two-independent sample, Satterthwaite t-test to test for superiority of iovera treatment to Standard of Care treatment, with a significance level of 0.025, assuming a 1:1 allocation to treatment, a true treatment effect ( $\mu_{1,Active} - \mu_{1,SOC}$ ) of -12.0 mg, and true standard deviations of 18.2 mg and 26.0 mg, for the iovera and Standard of Care treatments, respectively. Based on these specifications, the required sample size is 57 subjects per treatment group, for a total of 114 subjects. To account for a small number of subjects withdrawing early or not having data available for the analysis of the primary effectiveness endpoint, the required sample size was increased to 120 randomized subjects (approximately 60 Active Treatment subjects and 60 Standard of Care Treatment subjects).

### **3.5 Changes to the Protocol-Specified Analyses**

For the analyses of the primary effectiveness endpoint and the first secondary effectiveness endpoint, missing data will be imputed using multiple imputation methods. The protocol states that t-tests will be performed on the imputed datasets and the results will be summarized using PROC MIANALYZE. Instead, the difference in means between treatments and the corresponding standard error will be obtained for each imputed dataset and PROC MIANALYZE will be used to summarize the results and produce t-tests.

## **4.0 EFFECTIVENESS AND SAFETY ENDPOINTS**

### **4.1 Primary Effectiveness Endpoint**

The primary effectiveness endpoint is the cumulative consumption of opioids from the time of hospital discharge to 6 weeks post-TKA Surgery. Opioid consumption will be converted to morphine equivalents, and subject consumption will be verified by pill count at follow-up visits. The cumulative morphine equivalent will be divided by the number of days to provide the Total Daily Morphine Equivalent (TME) for the subject.

### **4.2 Secondary Effectiveness Endpoints**

The secondary effectiveness endpoints are as follows:

1. AUC/time (see definition of AUC/time below) based on Changes from Baseline in KOOS JR. Scores through 6 weeks post-TKA
2. AUC/time based on Changes from Baseline through 6 weeks post-TKA in NRS for Pain
3. AUC/time based on Changes from Baseline through 6 weeks post-TKA in Timed Get Up and Go (TUG) test

Change in KOOS JR. scores from the Baseline visit to each post-baseline visit will be calculated for each subject as:

Change in KOOS JR. score =

Post-Baseline Visit KOOS JR. score – Baseline Visit KOOS JR. score,

such that a positive value indicates an increase in the KOOS JR. score, which is a positive outcome, while a negative value indicates a decrease, which is a negative outcome. Change in NRS for Pain scores from the Baseline visit to each post-baseline visit will be calculated for each subject as:

Change in NRS for Pain score =

Baseline Visit NRS for Pain score – Post-Baseline Visit NRS for Pain score,

such that a positive value indicates a decrease in the NRS for Pain score, which is a positive outcome, while a negative value indicates an increase, which is a negative outcome. Change from baseline in the TUG test is defined analogously to the change from baseline in NRS for Pain score. The first and key secondary effectiveness endpoint, AUC/time based on Changes from Baseline in KOOS JR. scores through 6 weeks post-TKA, is the area under the curve (AUC) of Change in KOOS JR. scores from the Baseline visit through the 6-week visit divided by the number of days from TKA until the 6-week visit. AUC will be calculated using the trapezoidal rule and the changes in the KOOS JR. score at the following time points: Baseline (change=0), 72 hours, 2 weeks, and 6 weeks post-TKA. The second and third secondary effectiveness endpoints are defined analogously.

[REDACTED]

[REDACTED]

[REDACTED]

[REDACTED]

- [REDACTED]
- [REDACTED]
- [REDACTED]

#### **4.4 Safety Endpoints**

The safety endpoints are as follows:

- All treatment emergent adverse events

## **5.0 STATISTICAL CONSIDERATIONS**

### **5.1 General Methodology**

The statistical analysis of the data obtained from this study will be performed using SAS® version 9.4 or higher. All statistical tests will be performed at the 0.05 significance level, unless otherwise noted.

The data collected in this study will be documented using summary tables and subject data listings. Continuous variables will be summarized using descriptive statistics, specifically the number of observations, mean, median, standard deviation, minimum and maximum. Categorical variables will be summarized by frequencies and percentages.

Data listings will be sorted by treatment group and subject number, and Study Day (Day of TKA = Day 0), if appropriate. All date fields will be presented in a format of yyyy-mm-dd (e.g., 2018-01-31 for January 31, 2018) in the listings.

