10.2 General

Categorical data will be summarized using frequency tables, presenting subject counts and percentages. Continuous variables will be summarized using descriptive statistics (number of subjects, mean, standard deviation, median, minimum, and maximum).

The SAS system will be used to perform all statistical analyses.

Exact binomial confidence intervals will be generated for proportions. Confidence intervals based on the t-distribution will be generated for means and differences of means. Fixed sequential testing will be performed to control the overall Type I error rate.

Except where noted otherwise, within-subject change-from-baseline (pre-treatment baseline) values for a variable are calculated as:

$$\text{Change-from-Baseline} = \text{Follow-Up value} - \text{Pre-Treatment value},$$

such that a positive value indicates an increase from the pre-treatment value to the follow-up value, whereas a negative value indicates a decrease.

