### **5.6 Multiple Comparisons / Multiplicity**

The fixed sequential testing procedure will be used for the comparison of the two treatments with respect to the first (and key) secondary effectiveness endpoint. Therefore, for this endpoint, the analysis comparing the two treatments will be formally conducted only if the analysis for the primary effectiveness endpoint yields a statistically significant result. For informational purposes, however, the results of the analyses (i.e., p-value) will be presented regardless of the results for the primary effectiveness endpoint.

No adjustments for multiplicity will be made in the analyses.

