## 8.2 Secondary Effectiveness Endpoints

The secondary effectiveness endpoints are as follows:

1. AUC/time (see definition of AUC/time below) based on Changes from Baseline in KOOS JR. Scores through 6 weeks post-TKA.  
KOOS JR. Scores range from 0 (total knee disability) to 100 (perfect knee health).
2. AUC/time based on Changes from Baseline through 6 weeks post-TKA in NRS for Pain (both pain in the last 7 days and pain right now)  
NRS Pain ratings range from 0 (no pain) to 10 (worst pain imaginable).
3. AUC/time based on Changes from Baseline through 6 weeks post-TKA in Timed Get Up and Go (TUG) test.  
The TUG test measures, in seconds, the time it takes to raise from sitting, walk 10 feet, turn around, walk back and sit back down.

Change in KOOS JR. scores from the Baseline visit to each post-baseline visit will be calculated for each subject as:

$$\text{Change in KOOS JR. score} = \text{Post-Baseline Visit KOOS JR. score} - \text{Baseline Visit KOOS JR. score},$$

such that a positive value indicates an increase in the KOOS JR. score, while a negative value indicates a decrease. The first and key secondary effectiveness endpoint, AUC/time based on Changes from Baseline in KOOS JR. scores through 6 weeks post-TKA, is the area under the curve (AUC) of Change in KOOS JR. scores from the Baseline visit through the 6-week visit divided by the number of days from TKA until the 6-week visit. AUC will be calculated using the trapezoidal rule and the changes in the KOOS JR. score at the following time points: Baseline (change=0), 72 hours, 2 weeks, and 6 weeks post-TKA. Scoring instructions for the KOOS JR. English Version 1.0 are provided in Appendix 1.

The difference in mean AUC/time between the two treatment groups will be calculated as the mean Active AUC/time – the mean Standard of Care AUC/time, such that a positive difference indicates that the Active Treatment group had a larger mean AUC/time based on Change in KOOS JR. score than the Standard of Care Treatment group, while a negative value indicates the opposite. Because a positive Change in the KOOS JR. score is indicative of pain relief, a positive difference between treatment groups reflects a positive outcome for this endpoint.

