Let  $\mu_{2,\text{Active}}$  and  $\mu_{2,\text{SOC}}$  denote the true mean AUC/time based on the Change from Baseline in KOOS JR. score from the Baseline visit through the six-week visit for the active and standard of care treatments, respectively. Then the null and alternative hypotheses for the test for non-inferiority for this endpoint are as follows:

$$H_0: \mu_{2,\text{SOC}} - \mu_{2,\text{Active}} \geq \delta$$

$$H_1: \mu_{2,SOC} - \mu_{2,Active} < \delta,$$

where the non-inferiority margin  $\delta=14$ .

Missing KOOS JR. data will be imputed using multiple imputation methods. First, the relatively uncommon, non-monotone missing data will be imputed using the MCMC option of SAS® PROC MI. The imputation model will include a term for treatment and the KOOS JR. score at visits 1, 4, 5, and 6. Second, the monotone missing values will be imputed using the chained equation method by SAS® PROC MI option MONOTONE REG. For each subject within each imputed dataset, the value of the endpoint will then be determined. The imputed data sets will each be analyzed to obtain the difference in means between treatments and the corresponding standard error, and the results will be summarized using PROC MIANALYZE (with THETA0=14, the non-inferiority margin, in the PROC MIANALYZE statement). The null hypothesis will be tested using a one-sided t-test. One of the secondary objectives of the study is to show that, over the 6-week post-TKA period, the Active Treatment group has similar levels of pain and functioning as compared to the Standard of Care Treatment group. This objective will be met if the t-test for non-inferiority is statistically significant using a 0.025 level of statistical significance.

There is one item in the KOOS JR. scale (Knee Twisting/Pivoting) with a large number of missing responses. Prior to undergoing multiple imputation, missing values for this item will be imputed by performing a linear regression (SAS PROC GLM) on the other 6 KOOS JR. items and imputing the Knee Twisting/Pivoting score for each patient with a missing value based on the estimated linear regression line. At baseline this imputation will be performed across treatment arms; at post-baseline time points the imputation will be performed by treatment arm.

Change in NRS for Pain scores and TUG test scores from the Baseline visit to each post-baseline visit will be calculated for each subject as:

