$$\text{Change score} = \text{Baseline Visit score} - \text{Post-Baseline Visit score},$$

such that a positive value indicates a decrease in the score (which is a positive outcome), while a negative value indicates an increase (which is a negative outcome). AUC/time for these endpoints will be calculated in the same way described above for KOOS JR.

Each secondary effectiveness endpoint will be summarized by treatment using descriptive statistics. For each treatment, the null hypothesis that the true mean AUC/time equals zero will be tested using a paired t-test. Ninety-five percent confidence intervals based on the t-distribution for the true mean AUC/time for each treatment and for the true difference in these means between treatments will be provided. For the second and third secondary effectiveness endpoints, a one-sided, two-sample t-test will be used to test the null hypothesis that the iovera mean is less than or equal to the Standard of Care mean versus the alternative hypothesis that the iovera mean is greater than the Standard of Care mean. In addition, for each secondary effectiveness endpoint, the initial result (e.g., KOOS JR. score at 6-weeks post-TKA), as well as the Change from Baseline value, will be summarized by treatment group at each visit at which data for the endpoint are collected using descriptive statistics, together with 95% confidence intervals for the mean based on the t-distribution. The estimated difference in the mean change from baseline between the two treatment groups and a 95% confidence interval based on the t-distribution for the true difference in these means between the two treatments will also be provided.

The fixed sequential testing procedure will be used for the comparison of the two treatments with respect to the first (and key) secondary effectiveness endpoint. Therefore, for this endpoint, the analysis comparing the two treatments will be formally conducted only if the analysis for the primary effectiveness endpoint yields a statistically significant result. For informational purposes, however, the results of the analyses (i.e., p-value) will be presented regardless of the results for the primary effectiveness endpoint.

These analyses will be performed for the ITT Population.

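### The SAP adds one-sided NRS and TUG comparisons with no stated level, so the 0.05 default literally applies: twice the one-sided 0.025 used elsewhere and out of step with the 95% intervals beside them

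*SAP*

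**What the plan says.** **Protocol.** Section 10.2 commits the trial to a gatekeeping approach: "Fixed sequential testing will be performed to control the overall Type I error rate". Section 10.4.2 applies that sequence to the key secondary endpoint (KOOS JR.), after the primary. For every secondary endpoint it plans a within-arm test against zero, plus 95% confidence intervals for each arm and for the between-arm difference. It names no between-arm test for NRS or TUG.

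**SAP.** Section 8.2 adds one: "For the second and third secondary effectiveness endpoints, a one-sided, two-sample t-test will be used to test the null hypothesis", with the alternative that iovera is better. The same section covers two NRS items ("both pain in the last 7 days and pain right now"), so there are three such tests at 6 weeks. The footnotes to the shells for Tables 2 and 5 print these p-values.

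**Levels.** For KOOS JR., SAP 8.2 is explicit: "This objective will be met if the t-test for non-inferiority is statistically significant using a 0.025 level of statistical significance". SAP 8.1 gives 0.025 for the one-sided primary test, and SAP 3.4 sizes the trial "with a significance level of 0.025, assuming a 1:1 allocation to treatment". For NRS and TUG no level is given, which leaves the general rule in SAP 5.1: "All statistical tests will be performed at the 0.05 significance level, unless otherwise noted". That rule does not say whether 0.05 is one-sided or two-sided.

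**Multiplicity.** SAP 5.6 states the scope of the sequence: "The fixed sequential testing procedure will be used for the comparison of the two treatments with respect to the first (and key) secondary effectiveness endpoint". It then closes with "No adjustments for multiplicity will be made in the analyses".

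**Labelling.** SAP 3.5, the list of changes from the protocol analyses, mentions only how multiply imputed results are combined. SAP 8.4 marks the by-visit two-sided NRS tests as post hoc. The added AUC/time tests carry no such label.

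**The concern.** Wherever the SAP attaches a level to a one-sided test, it is 0.025. The NRS and TUG tests are one-sided with no level, so a programmer following the text would judge them at 0.05. In Table 2 they would share that 0.05 with two-sided tests, which makes them twice as lenient in the favourable direction. They would also disagree with the two-sided 95% intervals printed in the same table.

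The tests can be read as significant even if the primary and KOOS JR. tests fail, and nothing tells the reader that they lie outside the error control described in Protocol 10.2. The trial is unblinded (SAP 3.3) and two of the three tests use self-reported pain, so a favourable nominal p-value here is easy to over-read.

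**Working it through.** **Plan's own figure.** The documents give no error rate for the NRS and TUG tests, so there is none to reproduce. The level used for the primary can be checked through SAP 3.4 (difference 12.0 mg, SDs 18.2 and 26.0, 57 per arm, at least 80% power):

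- standard error = √((18.2² + 26.0²)/57) = √(1007.24/57) = 4.20
- non-centrality = 12.0/4.20 = 2.85
- Satterthwaite power at one-sided 0.025 = 80.7%; the smallest adequate size is 56 per arm.

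The stated 57 is consistent with one-sided 0.025.

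**Step 1: per-test level.** Literal default over stated one-sided level: 0.05/0.025 = 2.

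**Step 2: test against interval.** With about 60 + 60 − 2 = 118 degrees of freedom:

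- a one-sided 0.05 test rejects when t exceeds about 1.66
- the two-sided 95% interval excludes zero in the favourable direction only when t exceeds about 1.98.

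Any t between 1.66 and 1.98 is nominally significant while its interval includes zero. With no true difference, that happens with probability 0.05 − 0.025 = 2.5% per test.

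**Step 3: chance of at least one nominally significant result at 6 weeks.** The inputs are three tests (two NRS items and TUG), all nulls true, no gating and no adjustment. The documents give no correlation between the test statistics, so it is an assumption and is shown as a range. Under independence the rate is 1 − (1 − α)³:

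- α = 0.05: 1 − 0.95³ = 14.3%
- α = 0.025: 1 − 0.975³ = 7.3%

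For correlated tests the rate is 1 minus the trivariate normal probability that all three statistics stay below the critical value:

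| Equal pairwise correlation (assumed) | One-sided 0.05 each | One-sided 0.025 each |
|---|---|---|
| 0 | 14.3% | 7.3% |
| 0.3 | 13.0% | 6.8% |
| 0.5 | 11.8% | 6.3% |
| 0.7 | 10.3% | 5.5% |
| 0.9 | 8.0% | 4.2% |
| 1 (limit) | 5% | 2.5% |

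The two NRS items may well correlate more with each other than with TUG. With NRS–NRS correlation from 0.5 to 0.95 and NRS–TUG from 0 to 0.5, the rates are 9.9% to 13.3% at 0.05 and 5.2% to 6.9% at 0.025.

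**Step 4: scope.** SAP 8.4 applies the same analysis at 72 hours (NRS but not TUG), 2 weeks and 12 weeks. That makes 2 × 4 = 8 NRS tests and 3 TUG tests, 11 in all. The rates above cover the three 6-week tests only; across all 11 the rate would be higher.

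**The case against.** **The level.** SAP 5.1 does not state sidedness. Every one-sided level the SAP states is 0.025, and the 95% intervals match 0.025, so the author may have had a conventional two-sided 0.05 in mind. On that reading nothing is doubled and the clash with the intervals disappears. This stands: a reader might infer that the SAP deliberately chose one-sided 0.05, but the documents support only that the literal text leads there and that the intention is unclear.

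**The rate.** A reader might take the table to mean a 10% to 14% chance of a false secondary claim. The documents do not support that. SAP 8.1 and 8.2 attach a met-or-not-met rule only to the primary and KOOS JR. endpoints, and Protocol 10.7 rests overall study success on the primary results. The figure also needs one-sided 0.05, all three nulls true, and an equal correlation of about 0.7 or less.

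**The sequence.** A reader might infer that the SAP took NRS and TUG out of a protocol sequence. It did not: Protocol 10.4.2 already limits the sequence to the key secondary endpoint, and the SAP repeats that scope. Leaving non-key secondary endpoints unadjusted is an accepted choice when they carry no claim.

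**Pre-planning.** Protocol 10.1 says treatment effects on NRS and TUG will be investigated, and 10.4.2 plans intervals for the between-arm differences. The SAP therefore adds a directional p-value, not the comparison itself.

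These arguments limit what follows from the gap; they do not close it. The level remains unstated, the literal default conflicts with the rest of the SAP, and the tests are neither listed as additions nor labelled.

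**Conclusion.** The concern holds as a defect of specification. The one-sided NRS and TUG tests have no stated level; taken literally they run at 0.05, twice the level of the other one-sided tests and inconsistent with their own 95% intervals. They are ungated, unadjusted and missing from SAP 3.5.

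The size depends on how SAP 5.1 is read. At one-sided 0.05, the chance of at least one nominally significant 6-week result is 14.3% under independence, 11.8% at equal correlation 0.5 and 8.0% at 0.9, with a limit of 5%. At one-sided 0.025 it is about 4% to 7% over the same range of correlations. Both assume that all three nulls are true, and the correlations are assumed. The primary and KOOS JR. conclusions are unaffected. The point should be fixed, but the trial's main result does not depend on it.

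**What to change.** 1. In SAP 8.2, state that the NRS and TUG between-arm tests use one-sided 0.025. SAP 8.4 then inherits this by reference.
2. In SAP 3.5, list these tests as additions to the protocol analyses.
3. In SAP 8.2 and the footnotes to Tables 2 and 5, label their p-values as supportive and outside type I error control.
4. Reword the last sentence of SAP 5.6 to say that no adjustment is made beyond the fixed sequence for the primary and KOOS JR. endpoints.

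This aligns the tests with their intervals. It does not bring the three-test rate down to 2.5%; it stays at about 4% to 7%, which is why the label is needed.

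Extending the fixed sequence to NRS and TUG at one-sided 0.025 is optional. It would hold the whole sequence to at most 2.5% but needs a justified order. The past-7-days NRS item would be a doubtful first step, because at the 72-hour call its recall window reaches back before surgery.

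The cost is a few sentences in SAP 3.5, 5.6 and 8.2 and in the table footnotes, with no new data or subjects. Nominal significance on NRS and TUG becomes harder to reach than under the literal 0.05.
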